10.0 STATISTICAL CONSIDERATIONS

10.1 Study Design/Study Endpoints

This is a single arm two-stage Simon optimum Phase II study of pazopanib and topotecan with progression-free rate at 12 weeks as the primary outcome. The historic PD free rate at 12 weeks for single agent pazopanib is 55%. To detect a 20% improvement (an 11% absolute improvement) with the combination of pazopanib and topotecan in a single-arm two-stage optimum design and a one-tailed exact binomial p- value, a total of 92 evaluable STS patients is required to detect 55% vs 66% with 80%

power and an alpha level of 10%. If 32 out of the first 55 patients are alive and progression free at 12 weeks, the trial may enroll up to 108 patients in order to acquire a total of 92 evaluable patients. At that time, if 56 or more out of 92 are alive and progression-free at 12 weeks, then the trial will conclude that the true 12 week PFS rate is at least 66%. There is a 63% probability of terminating the study after the first stage when the true rate is 55%. See sections 6.0 and 7.0 for definitions of evaluable patients for response and adverse event information.

Osteosarcoma/Liposarcoma exploratory group:

Up to 36 patients with osteosarcoma and 20 patients with liposarcoma will be enrolled to obtain exploratory information for patients with these two histologies. Although the sample sizes in these two cohorts were selected for feasibility rather than to power a specific hypothesis, 56 subjects will provide estimates of PFR and OS with sufficient precision to support additional study of pazopanib in these patients.

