10.2 Sample Size and Accrual

A total of 92 evaluable STS patients is required to detect 55% vs 66% with 80% power and an alpha level of 10%. If 32 out of the first 55 patients are alive and progression free at 12 weeks, this trial may enroll up to 108 STS patients in order to accrue a total of 92 evaluable patients. If the trial has not yet achieved 32 responses, may be suspended to enrollment to allow the 55th patient to reach week 12 of treatment for evaluation.

In addition, up to 36 patients with osteosarcoma and 20 patients with liposarcoma will be enrolled to obtain exploratory information for patients with these two histologies. Data exists to help construct baseline event free survival outcomes that can be used as a comparison for future phase II trials for recurrent osteosarcoma ([J Clin Oncol](#). 2016 Sep 1;34(25):3031-8. doi: 10.1200/JCO.2015.65.5381. Epub 2016 Jul 11.)

Using a single arm, 2 stage Phase II trial design: For stage I- If 4 or more of 19 patients have disease control of greater than 4 months then Stage 2 should be opened. The endpoint is that if 11 or more patients/ 36 have disease control at 4 months, then the agent is considered sufficiently efficacious for additional study.

As the study has been using 12 week and 20 week endpoints, we can use 20 weeks instead of 16 weeks as a surrogate endpoint.

The DMC reviewed the interim analysis data on 1/11/2017, and has approved cohort 1 to reopen to 96 total patients(to obtain 92 evaluable patients). In addition, based on the percentage of non-evaluable patients during the interim analysis, it was determined that a total of 108 patients would most likely need to be enrolled in order to obtain 92 evaluable patients.

The remaining slots have been equally divided in 5 ways among the sites, with an expiration date of May 12, 2017. Status of accrual will be reassessed at that time, and the remaining slots will be divided accordingly.

The 16 additional osteosarcoma slots will only be available at Northwestern (NMH).

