10.3 Data Analyses Plans

PFR and OS will be estimated for each histologic group (STS, osteosarcoma, and liposarcoma) using Kaplan-Meier methods. Response rates will be summarized by the observed proportion of patients with response, along with a 95% confidence interval. Toxicities will be tabulated and summarized by the number of patients experiencing each toxicity. A formal hypothesis test for the median PFR of the STS patients is planned; no formal hypothesis test is planned for the other two histologic groups.

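### Section 10 does not say how the STS p-value, confidence limit and 12-week rate allow for the stage-1 stop, and two-stage inference will agree with the decision only if the printed cut-off of 56/92 is also reconciled with the stated 10% alpha.

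*Combined protocol and SAP*

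**What the plan says.** Section 10.1 sets the design: "This is a single arm two-stage Simon optimum Phase II study of pazopanib and topotecan with progression-free rate at 12 weeks as the primary outcome". Its null is given as "The historic PD free rate at 12 weeks for single agent pazopanib is 55" percent. Section 10.2 gives the size: "A total of 92 evaluable STS patients is required to detect 55% vs 66% with 80% power and an alpha level of 10" percent. The p-value is mentioned once, in the sample-size sentence of 10.1 (repeated in the Study Summary): "in a single-arm two-stage optimum design and a one-tailed exact binomial" p-value.

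The decision rules in 10.1 are counts. Stage 2 opens on this condition: "If 32 out of the first 55 patients are alive and progression free at 12 weeks". Success is declared "if 56 or more out of 92 are alive and progression-free at 12 weeks". The stage-1 stop has a stated probability: "There is a 63% probability of terminating the study after the first stage when the true rate is 55" percent.

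Section 10.3 is the only analysis section: "PFR and OS will be estimated for each histologic group (STS, osteosarcoma, and liposarcoma) using Kaplan-Meier methods". It attaches the observed proportion with a 95% interval to response rates, not to PFR. The one formal STS test it names concerns median PFR, not the 12-week rate. It does not mention the two stages. Section 10.2 records that the DMC reviewed the interim data and let the STS cohort reopen, so the trial did pass stage 1.

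**The concern.** The stated alpha, power and early-termination probability belong to a procedure with a stage-1 stop. A p-value, confidence limit or estimate calculated as if the 92 patients were a single sample belongs to a different procedure. Two things are at stake.

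- **Consistency of the report.** An analyst who runs a standard exact binomial test on the final count can get p above 0.10 for a result that the two-stage design counts as a success. Section 10 gives no instruction that would prevent this.
- **The rate carried forward.** A trial that reaches stage 2 has been selected for a good stage 1. A pooled estimate keeps that selection. It matters most when the combination adds least, and a later trial would be planned from this figure.

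**Working it through.** **Inputs** (sections 10.1 and 10.2): p0 = 0.55, p1 = 0.66, one-sided alpha 0.10, power 0.80, n1 = 55, N = 92, so stage 2 has 92 − 55 = 37 patients. I read the stage-1 rule as continuing at 32 or more.

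**Formulas.** Let X1 ~ Bin(55, p), X2 ~ Bin(37, p) and S = X1 + X2.

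- Single-stage p-value at s: P(Bin(92, 0.55) ≥ s).
- Two-stage p-value at s: Σ over x1 = 32 to 55 of P(X1 = x1) × P(X2 ≥ s − x1), at p = 0.55. Outcomes are ordered by total successes, and any trial stopped at stage 1 ranks below every trial that continued.
- One-sided 90% lower limit: the p at which the chosen tail probability equals 0.10.

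**Step 1: reproduce the plan's figures.** P(X1 ≤ 31) at 0.55 is 0.631, which matches the stated 63%. With success at 57 or more, alpha is 0.09998 and power at 0.66 is 0.803, which match 10% and 80%. With success at 56 or more, as printed, alpha is 0.136 and power 0.843. The stated alpha therefore belongs to 57.

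**Step 2: compare the two p-values near the boundary.**

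| Final count | Single-stage p | Two-stage p | Lower 90% limit, single-stage | Lower 90% limit, two-stage |
|---|---|---|---|---|
| 56/92 | 0.152 | 0.136 | 0.537 | 0.540 |
| 57/92 | 0.108 | 0.09998 | 0.548 | 0.550 |
| 58/92 | 0.073 | 0.070 | 0.559 | 0.560 |
| 59/92 | 0.048 | 0.047 | 0.570 | 0.571 |

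The single-stage value is always the larger, because it also counts paths that reach s from fewer than 32 at stage 1, which the stop removes. At 57 the two fall on opposite sides of 0.10, and the limits fall on opposite sides of 0.55 (the two-stage limit is 0.55001). From 58 upward they agree. At 56 they also agree with each other, but both contradict the printed success rule.

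If success were judged by single-stage p < 0.10, the trial would need 58/92. Under the two-stage design that has alpha 0.070 and power 0.749. The chance of finishing on exactly 57 is 0.09998 − 0.07007 = 3.0% at a true 55%, and 0.8028 − 0.7493 = 5.4% at a true 66%.

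**Step 3: bias of the pooled rate given continuation.** The expected pooled rate is (E[X1 | X1 ≥ 32] + 37p)/92. This takes the Kaplan-Meier estimate at week 12 as equal to the simple proportion, which holds if nobody is censored before week 12.

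| True rate | P(continue) | E[X1 given X1 ≥ 32] | Expected pooled rate | Bias given continuation | Unconditional bias |
|---|---|---|---|---|---|
| 55% | 0.369 | 34.03 | (34.03 + 20.35)/92 = 59.1% | +4.1 points | −1.0 |
| 60% | 0.663 | 35.02 | (35.02 + 22.20)/92 = 62.2% | +2.2 points | −1.0 |
| 66% | 0.912 | 36.93 | (36.93 + 24.42)/92 = 66.7% | +0.7 points | −0.4 |

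The last column averages over trials that stop (rate X1/55) and trials that continue (rate S/92).

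**Step 4: what adjusted estimates do at 57/92.** The raw rate is 0.620. The estimator unbiased over the whole two-stage design (UMVUE) gives 0.630, and the one unbiased given continuation gives 0.604. The direction of the correction depends on the target. The stage-2 rate is free of stage-1 selection, but with 37 patients its standard error is √(0.66 × 0.34/37) = 0.078, or 0.082 at a true 55%.

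**The case against.** The strongest reply is that no wrong method is written down. A reader might infer that the plan prescribes a single-stage p-value. The documents do not support that: the phrase stands in a sample-size sentence, is attached to the two-stage design, and sits beside figures for early termination, alpha and power that an exact two-stage calculation reproduces with 57. The defect is a method left unspecified.

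The decision is also a count. No section declares success when p is below 0.10, so the 58/92 threshold and the 74.9% power describe a rule that the protocol does not contain. They show what follows if someone judges the result by an ordinary binomial p-value. A reader might further fear more false positives from such a p-value. It is conservative, so the risk is lost power or a contradictory report.

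On the estimate, a reader might conclude that the pooled rate is simply too high. That holds only given continuation; over all outcomes of the design it is slightly low, and the usual unbiased estimator would move 57/92 upward. Even conditionally, the bias at the design alternative is 0.7 points.

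All of this stands and limits the point. It does not remove it: section 10 names no two-stage p-value, limit or estimator, and the trial is known to have continued, which makes the conditional view relevant.

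**Conclusion.** The point holds as an omission that should be corrected. Sections 10.1 and 10.3 leave open how STS inference allows for the stage-1 stop. The choice alters the reading of one count at or above the 10% boundary, 57/92 (0.108 against 0.09998), and the single-stage choice errs on the safe side. The printed cut-off is the larger discrepancy: at 56/92 the rule declares success while both p-values exceed 0.10, and its alpha is 13.6% against the stated 10%. Two-stage inference alone would not remove that contradiction. Given continuation, the pooled rate overstates by between 4.1 points (true 55%) and 0.7 points (true 66%). The 4.1 points are over a third of the 11-point improvement sought, but they arise only if the combination adds nothing.

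These results assume continuation at 32 or more of 55, exactly 55 and 92 evaluable patients at the two looks, and no censoring before week 12.

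**What to change.** In sections 10.1 and 10.3:

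1. State that the p-value and one-sided 90% lower limit for the STS 12-week rate come from the two-stage sample space: continuation at 32 or more of 55, outcomes ordered by total successes.
2. Reconcile the success cut-off with the stated 10% alpha. On the plan's own figures that is 57 or more of 92. The p-value, the limit and the decision then agree at every count.
3. Keep the pooled rate as the headline. Report beside it either the stage-2 rate or a conditionally unbiased estimate as a check. Say that the target is the rate given continuation, and that the stage-2 rate rests on only 37 patients, with a standard error of about 8 points.

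This costs a few lines of text and a short program, with no new patients or data. The check estimate may look less favourable than the headline, and a final count of exactly 56 would no longer be a success. If the 12-week counts are already known when the change is made, the report should say so.

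### The final success cut-off of 56 of 92 gives a one-sided type I error of 13.6%, not the stated 10%; the stated figures belong to 57 of 92

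*Combined protocol and SAP*

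**What the plan says.** Section 10.1 sets out the primary analysis for the soft tissue sarcoma cohort: "This is a single arm two-stage Simon optimum Phase II study of pazopanib and topotecan with progression-free rate at 12 weeks as the primary outcome". Its null rate is the single-agent figure: "The historic PD free rate at 12 weeks for single agent pazopanib is 55" per cent. The test is based on "a one-tailed exact binomial p- value". Section 10.2 gives the targets: "A total of 92 evaluable STS patients is required to detect 55% vs 66% with 80% power and an alpha level of 10" per cent.

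The stage 1 rule in Section 10.1 reads "If 32 out of the first 55 patients are alive and progression free at 12 weeks", in which case enrolment goes on until 92 patients are evaluable. Section 10.2 treats 32 as sufficient, since it refers to the case "If the trial has not yet achieved 32 responses". At the end, success is declared "if 56 or more out of 92 are alive and progression-free at 12 weeks". Section 10.1 adds one operating characteristic: "There is a 63% probability of terminating the study after the first stage when the true rate is 55" per cent.

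The Study Design row of the Study Summary repeats the same rule and the same figures. No other section gives a different final cut-off.

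**The concern.** A two-stage design has two integer cut-offs, and together with the stage sizes they fix the type I error and power exactly. The stated cut-offs can therefore be checked against the stated 10% and 80%. A cut-off that is low by one would let the trial claim success at a count that its own alpha does not allow.

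This is the final-stage success rule for the primary endpoint, in a single-arm trial with no concurrent control and an alpha that is already generous. If the rule stays as written, a result of exactly 56 of 92 would be reported as positive at the 10% level when it is not.

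**Working it through.** **Inputs (Sections 10.1 and 10.2)**
- Null rate p0 = 0.55; alternative p1 = 0.66.
- One-sided alpha 0.10; power 0.80.
- Stage 1: n1 = 55, continue if X1 ≥ 32.
- Final: N = 92, so stage 2 has 92 − 55 = 37 patients; success if X1 + X2 ≥ c, with c = 56 as stated.

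**Formulas**
- Early termination under the null: P(X1 ≤ 31), with X1 ~ Bin(55, 0.55).
- Probability of declaring success at true rate p: sum over x = 32, …, 55 of P(X1 = x | 55, p) × P(X2 ≥ c − x | 37, p). At p = 0.55 this is the type I error; at p = 0.66 it is the power.

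**Step 1: reproduce the plan's early-termination figure.** P(X1 ≤ 31) = 0.6309, which matches the stated 63%. This confirms that 32 is enough to continue.

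**Step 2: the final cut-off as written, and one higher**

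| Success if | Type I error (p = 0.55) | Power (p = 0.66) |
|---|---|---|
| ≥ 56 of 92 | 0.1358 | 0.8431 |
| ≥ 57 of 92 | 0.09998 | 0.8028 |

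The excess at 56 over the stated alpha is 0.1358 − 0.10 = 0.0358, or 36% in relative terms.

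**Step 3: is there a reading under which 56 gives 10%?**

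| Reading, with success at ≥ 56 | Type I error | Early termination under 55% |
|---|---|---|
| Continue at ≥ 31 | 14.5% | 52.5% |
| Continue at ≥ 32 (as stated) | 13.6% | 63.1% |
| Continue at ≥ 33 | 12.1% | 72.8% |
| Interim look ignored | 15.2% | not applicable |

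Every reading exceeds 10%, and only the stated stage 1 rule gives 63%.

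**Step 4: which cut-offs fit?** A search over all pairs of cut-offs with n1 = 55 and N = 92 finds one pair with alpha ≤ 0.10 and power ≥ 0.80: continue at ≥ 32, succeed at ≥ 57.

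**Likely cause (inference).** Simon designs are usually tabulated as r1/n1 and r/N, where r is the largest count that does not reject the null. Here that would be 31/55 and 56/92. The first boundary was converted to 32; the second seems to have been copied without adding one. The arithmetic does not depend on this explanation.

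**The case against.** The arithmetic itself is not open to dispute. The objections concern weight and remedy.

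- **Only one outcome is affected.** The two cut-offs differ only if the trial continues and ends at exactly 56. That has probability 0.1358 − 0.09998 = 3.6% at a true rate of 55%, and 0.8431 − 0.8028 = 4.0% at 66%. The interim decision and the sample size are untouched. This stands, and it limits the practical effect.
- **Power is not contradicted.** If 80% is a minimum, 84.3% satisfies it. This also stands: the conflict is with alpha alone.
- **The timing is late.** The interim data were reviewed in January 2017, and Appendix H records that cohort 1, and later the whole study, closed to accrual. Moving a success threshold now could look data-driven. This bears on how the correction is made, but does not make the stated alpha true.
- **57 is itself tight.** It meets 10% by about 0.00002, and only with exactly 92 evaluable patients. Keeping the stage 1 rule, 57 of 93 gives 12.0% and 56 of 91 gives 11.5%. An exact p-value that ignored the interim look would be 0.108 at 57 of 92. Section 6.3 lets the evaluable number depend on exclusions approved by the DMC. These points stand as reasons to fix the denominator and name the two-stage test; they do not support 56.

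**Conclusion.** The final cut-off contradicts the stated alpha. As written, the rule has a one-sided type I error of 13.6% instead of 10% (3.6 percentage points too high) and power of 84.3%. The stated 10%, 80% and 63% are all met by success at 57 or more of 92. The result rests on the plan's own inputs: independent binomial outcomes, stage 1 of 55 with at least 32 to continue, binding stopping at stage 1, and exactly 92 evaluable patients. Relaxing the stage 1 rule or ignoring the interim look raises the type I error under the 56 cut-off further. The inconsistency must be resolved because it sits in the primary success rule, although it changes the conclusion only at exactly 56 successes.

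**What to change.** Make one of two changes, identically in the Study Summary (Study Design row) and in Section 10.1:

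1. Set the final success cut-off at 57 or more of 92 and keep the stated alpha of 10% and power of 80%. Power falls from 84.3% to 80.3%, which still meets the target.
2. Keep 56 or more of 92 and restate the one-sided alpha as 13.6% and the power as 84%. Section 10.2, which repeats the 10% and 80%, must then change as well.

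In either case, date the change and state whether the cohort 1 week-12 results were known when it was made. If they were, report the true 13.6% and 84.3% for the written rule, together with the conclusion under 57. Also state that the test accounts for the interim look, and how the cut-off will be set if the evaluable number is not 92.

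The cost is a small text change with a dated justification. No patients or data are added.

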6.2 Antitumor Effect

For the purposes of this study, patients should be re-evaluated for response at 6 weeks, 12 weeks and then every 2 cycles thereafter. In addition to a baseline scan, confirmatory scans should also be obtained a minimum of 4 weeks following initial documentation of objective response. The investigator may opt to have the follow up scan performed according to the schedule (without an extra scan) as this follows the intent of the RECIST guidelines.

Response and progression will be evaluated in this study using the Response Evaluation Criteria in Solid Tumors (RECIST) Committee, version 1.1.64 Changes in only the largest diameter (unidimensional measurement) of the tumor lesions are used in the RECIST criteria, as defined below. In contrast, measurable disease in lymph nodes is determined based on the lymph node short axis.

6.3 Valuable for objective response:

All patients enrolled in the study should be assessed for response to treatment, even if there are major protocol treatment deviations or patients exhibit objective disease progression prior to the end of cycle 1.

All conclusions should be based on all enrolled patients. Subanalyses may then be performed on the basis of a subset of patients, excluding those for whom major protocol deviations have been identified (e.g., early death due to other reasons, early discontinuation of treatment, treating an ineligible patient, major protocol violations, etc.). However, these subanalyses may not serve as the basis for drawing conclusions concerning treatment efficacy, and the reasons for excluding patients from the analysis should be clearly reported. The 95% confidence intervals for response rate should also be provided.

All patients who were enrolled on the trial should be included in the main analysis of the response rate. Thus, an incorrect treatment schedule or drug administration does not result in exclusion. However, if a patient is removed from treatment prior to their 12 week assessment for reasons other than disease progression or death, they will be considered non-evaluable for response if approved by the DMC.

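### The STS final cut-off of 56 of 92 misses the stated 10% type I error (57 meets it), and no cut-off is given for any other evaluable n

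*Combined protocol and SAP*

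**What the plan says.** Section 10.1 describes a two-stage test "in a single-arm two-stage optimum design and a one-tailed exact binomial" calculation. The null is "The historic PD free rate at 12 weeks for single agent pazopanib is 55" (per cent). Section 10.2 gives the target: "A total of 92 evaluable STS patients is required to detect 55% vs 66% with 80% power and an alpha level of 10" (per cent).

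The first-stage rule reads "If 32 out of the first 55 patients are alive and progression free at 12 weeks"; if it is met, "the trial may enroll up to 108 patients in order to acquire a total of 92 evaluable patients". The final rule is success "if 56 or more out of 92 are alive and progression-free at 12 weeks". The stated chance of stopping after stage 1 at a true rate of 55% is 63%. The study summary repeats these rules.

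For the meaning of evaluable, section 10.1 refers to section 6.0. There, section 6.3 says of patients taken off treatment before the 12-week assessment for reasons other than progression or death that "they will be considered non-evaluable for response if approved by the DMC". The same section also says that conclusions are to rest on all enrolled patients. Section 10.2 presents 108 as the enrolment that would most likely be needed, projected from the non-evaluable share at the interim.

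Section 10.3 adds no cut-off for another denominator, no rule to analyse the first 92 evaluable patients, and no rule for a shortfall at the cap of 108.

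**The concern.** The primary conclusion depends on one count. If that count does not deliver the stated error rates, the trial runs a higher chance of a false positive than it declares.

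The count is also tied to a denominator that the trial does not fully control. Whether a patient is evaluable becomes known after entry and needs DMC approval, so the final n may be above or below 92. A fixed count is too easy to reach at a larger n and too hard at a smaller one. Without a written rule, someone must decide at analysis which patients to count or how to scale the cut-off. If outcomes are known by then, that is a data-dependent choice on the primary endpoint.

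**Working it through.** **Inputs (sections 10.1 and 10.2).** Null rate p0 = 0.55; alternative p1 = 0.66; stage 1 continues if X1 ≥ 32 of 55; final success if the total is at least c = 56 of n = 92; one-sided alpha 0.10; power 0.80; early stopping 0.63. I take the first 55 to be evaluable patients and treat the attained n as unrelated to outcome; the documents state neither.

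**Step 1: the plan's early-stopping figure.** P(X1 ≤ 31), with X1 ~ Bin(55, 0.55), is 0.6309. This matches the stated 63%, so the stage 1 rule is read correctly.

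**Step 2: the final rule.** The probability of declaring success is

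R(p; n, c) = Σ over x = 32 to 55 of P(X1 = x) × P(X2 ≥ c − x), with X1 ~ Bin(55, p) and X2 ~ Bin(n − 55, p).

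At n = 92:

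| c | R at 0.55 (type I error) | R at 0.66 (power) |
|---|---|---|
| 56 (printed) | 0.1358 | 0.8431 |
| 57 | 0.09998 | 0.8028 |

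The stated 10% and 80% are both reproduced with 57 and neither with 56.

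**Step 3: 56 kept at other attained n.**

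| n | Type I error | Power |
|---|---|---|
| 86 | 0.036 | 0.614 |
| 88 | 0.061 | 0.714 |
| 90 | 0.095 | 0.790 |
| 92 | 0.136 | 0.843 |
| 94 | 0.180 | 0.876 |
| 96 | 0.224 | 0.895 |
| 98 | 0.263 | 0.905 |
| 108 | 0.359 | 0.912 |

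A cut-off of 56 keeps type I error at or below 10% only for n ≤ 90, where power is below 80%.

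**Step 4: how far n might move.** This needs assumptions that the documents do not supply. Three illustrations:

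- All 108 enrolled, all evaluable patients counted, evaluable share 92/108 = 85.2%: SD = √(108 × 0.852 × 0.148) = 3.7; n is exactly 92 with probability 10.7%, below with 43.4%, above with 45.9%. At a share of 80%, n is above 92 with probability 6.7%; at 90%, with 92.9%.
- The 55 evaluable patients at the interim already settled. If they came from about 55/0.852 ≈ 65 enrolled, 43 remain: SD = √(43 × 0.852 × 0.148) = 2.3, 95% range 87 to 96, probability above 92 of 37%.
- Accrual stopped when 92 are evaluable: n = 92, or a little more if patients are still awaiting assessment.

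**The case against.** The strongest reply is that the random denominator matters little on average. Under the first illustration in step 4, keeping 56 at every n gives an average type I error of 14.2%, against 13.6% at exactly 92. Most of the excess over 10% therefore comes from the cut-off. That stands, and it is why the correction from 56 to 57 comes first. It does not remove the gap, because the trial is analysed at one n, and the error rate at that n may be far from the average.

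A reader might infer that the printed rule is sound at 92 and fails only elsewhere. It is not sound at 92 (step 2).

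A reader might also infer that the cut-off will probably be applied to the wrong denominator. The documents do not support that. Enrolment is allowed up to 108 for the purpose of reaching 92, accrual was to be reassessed along the way, and progression, death or removal can settle a patient's status before week 12. Accrual could have stopped near 92, or the first 92 evaluable could be analysed. What can be said is that no rule covers another n.

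Last, Appendix H records cohort 1, and later the whole study, as closed to accrual, so a table written now comes late. That is a fair caution. But the cut-offs follow from p0, the 10% level, the stage 1 rule and n alone, so they can be set without looking at outcomes.

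**Conclusion.** The point holds for the STS primary rule. The printed final cut-off gives 13.6% type I error and 84.3% power instead of 10% and 80%; 57 restores both. Separately, the plan lacks a cut-off for any evaluable n other than 92, and section 6.3 points to two different denominators, evaluable and all enrolled. The size of the second problem is conditional: between n = 86 and n = 98 a fixed 56 moves type I error from 3.6% to 26.3%, but which n was attained, and how likely each was, is not in the documents. The figures rest on 55 evaluable patients at stage 1 and on n being uninformative about outcome.

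A reader might extend the argument to the osteosarcoma cohort, where the rule is success "if 11 or more patients/ 36 have disease control at 4 months". The documents do not support that. The 36 are enrolled patients, section 10.1 says the cohort was sized for feasibility, no null, alternative, alpha or power is stated, and section 10.3 plans no formal test there. No declared error rate is lost.

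**What to change.** 1. In section 10.1 and the study summary, change the final cut-off at n = 92 from 56 to 57, and state openly that 56 did not meet the stated 10%.
2. State that every evaluable STS patient is counted in the primary decision. Reconcile this with the sentence in section 6.3 that bases conclusions on all enrolled patients, so that one analysis set governs the rule.
3. Before database lock, add the smallest final cut-off with exact two-stage type I error at or below 10%, keeping stage 1 at 32 or more of 55:

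| n | Cut-off | n | Cut-off | n | Cut-off |
|---|---|---|---|---|---|
| 84 | 53 | 93 | 58 | 102 | 63 |
| 85 | 53 | 94 | 59 | 103 | 64 |
| 86 | 54 | 95 | 59 | 104 | 64 |
| 87 | 55 | 96 | 60 | 105 | 65 |
| 88 | 55 | 97 | 60 | 106 | 65 |
| 89 | 56 | 98 | 61 | 107 | 66 |
| 90 | 56 | 99 | 62 | 108 | 67 |
| 91 | 57 | 100 | 62 | | |
| 92 | 57 | 101 | 63 | | |

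The same formula gives the cut-off if n falls below 84.

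4. State that the table depends only on n and was added after accrual closed.

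The cost is one table and some power. At n = 92 power goes from 84.3% to 80.3%. Across the table it runs from 73.8% (n = 87) and 74.4% (n = 84) to 83.3% (n = 106), and this range should be stated.

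### The primary decision rule attaches a claim of at least 66% to a test of 55%, and its cut-off of 56 of 92 gives a one-sided error of 13.6%, not the stated 10%

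*Combined protocol and SAP*

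**What the plan says.** Section 10.1 defines the design: "This is a single arm two-stage Simon optimum Phase II study of pazopanib and topotecan with progression-free rate at 12 weeks as the primary outcome". It gives the reference rate as follows: "The historic PD free rate at 12 weeks for single agent pazopanib is 55" per cent. The test is described as a "single-arm two-stage optimum design and a one-tailed exact binomial" test, and Section 10.2 gives the operating characteristics: "A total of 92 evaluable STS patients is required to detect 55% vs 66% with 80% power and an alpha level of 10" per cent.

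The stage 1 rule reads "If 32 out of the first 55 patients are alive and progression free at 12 weeks", in which case accrual continues to 92 evaluable patients. Section 10.1 puts the chance of stopping after stage 1 at 63% when the true rate is 55%. Success at the end is 56 or more of 92, and "then the trial will conclude that the true 12 week PFS rate is at least 66" per cent. The Study Design row of the Study Summary has the same rule and the same conclusion.

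Section 10.3 says: "Response rates will be summarized by the observed proportion of patients with response, along with a 95% confidence interval". For the progression-free rate it names Kaplan-Meier estimation and mentions no interval.

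**The concern.** There are two separate faults in the same sentence of the plan.

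The first is the conclusion. A test of 55% that rejects supports a rate above 55%. The 66% figure is the rate at which the design was given 80% power, and passing does not establish it. The rule can be passed with an observed rate well below 66%, so the pre-specified conclusion can contradict the trial's own estimate.

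The second is the cut-off. The stated alpha of 10% belongs to a final cut-off one patient higher than the one written.

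The first fault affects what would be claimed after any pass. The second affects whether the trial passes, but only at a final count of exactly 56. It also makes the stated alpha wrong whatever the count.

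**Working it through.** **Inputs (Sections 10.1 and 10.2).** n1 = 55, n = 92, so n2 = 37. Null rate 0.55, alternative 0.66. Continue if the stage 1 count X1 is at least 32. Succeed if the total is at least a, with a = 56 as written. One-sided exact binomial; stated alpha 10%, power 80%, early stopping 63% at a rate of 55%.

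**Formula.** With X1 ~ Bin(55, p) and X2 ~ Bin(37, p) independent,

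P(pass | p) = Σ over x from 32 to 55 of P(X1 = x) × P(X2 ≥ a − x).

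Alpha is this at p = 0.55, and power is this at p = 0.66.

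**Step 1: the plan's early-stopping figure.** P(X1 ≤ 31 | 55, 0.55) = 0.6309. This matches the stated 63% and confirms that stage 1 means at least 32.

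**Step 2: the stated errors.**

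| Final cut-off | Alpha (p = 0.55) | Power (p = 0.66) |
|---|---|---|
| 56 or more (as written) | 0.1358 | 0.8431 |
| 57 or more | 0.09998 | 0.8028 |
| 58 or more | 0.0701 | 0.7493 |

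With this stage 1 rule, 57 is the only final cut-off that meets both 10% and 80%. Other readings do not rescue 56: a stage 1 cut-off of 31 gives alpha 0.1447, a cut-off of 33 gives 0.1214, and a single-stage test on 92 patients gives 0.1522. An off-by-one slip is the likely source. The stage 1 figure of 32 is the smallest continuing count, while 56 looks like the largest failing count written as if it were a passing one.

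**Step 3: what a count of 56 shows.** The observed rate is 56/92 = 60.9%. The two-stage one-sided 90% lower bound solves P(pass with a = 56 | p) = 0.10 and equals 54.0%, so 55% is not excluded. At 57 the same bound is 55.0006%, which just excludes it. The 95% interval at 56/92 is 50.4% to 71.4% (two-stage, stagewise ordering) or 50.1% to 70.9% (single-stage Clopper-Pearson).

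**Step 4: how often the 66% claim would be wrong.**

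| True rate | P(pass), 56 or more | P(pass), 57 or more | P(pass with 56 to 60), written rule |
|---|---|---|---|
| 60% | 0.44 | 0.37 | 0.31 |
| 62% | 0.59 | 0.53 | 0.36 |
| 64% | 0.73 | 0.68 | 0.37 |

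Counts of 56 to 60 correspond to observed rates of 60.9% to 65.2%. A one-sided 90% lower bound of at least 66% would need 68/92 (73.9%), which is 68 − 56 = 12 patients more than the written cut-off. Moving from 56 to 57 lowers the pass probability but does not make the 66% statement true.

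**Step 5: how often the cut-off itself matters.** P(pass with exactly 56) is 0.1358 − 0.09998 = 0.036 at a true rate of 55%, 0.067 at 60% and 0.8431 − 0.8028 = 0.040 at 66%.

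**The case against.** The strongest reply is about weight. The plan openly states the 55% reference, the 55% versus 66% comparison, alpha and power, so a reader can see what is tested. The 66% sentence can be read as loose wording common in phase II screening, and it changes no pass or fail. The cut-off matters at one count only, with probability 3.6% to 6.7% at the rates shown. The likely overstatement is also modest: 6, 4 and 2 points at true rates of 60%, 62% and 64%. All of that is correct. Even so, the sentence is the pre-specified primary conclusion, it appears twice, and no other section corrects it.

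Four narrower points also have substance.

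- Section 10.2 calls the stage 1 progression-free count responses, so the 95% interval in Section 10.3 might be meant to cover the 12-week rate. The text is ambiguous. On either reading it names no interval that allows for the two stages.
- A two-sided 95% interval beside a one-sided 10% test can include 55% when the test rejects. At 57/92 it is 51.4% to 72.2%. This is ordinary practice, but the one-sided 90% bound should be shown beside it.
- At 57, alpha clears 10% by only 0.00002, and it holds for exactly 55 and 92 evaluable patients. Section 6.3 lets evaluability depend on committee approval, so the achieved numbers need to be checked.
- The interim review took place in January 2017, and Appendix H (Amendment 13) records that accrual is closed. A choice made blind to the final count may therefore be hard to demonstrate.

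**Conclusion.** Both faults stand, and this needs correction. As written, the rule has exact type I error 13.6% and power 84.3%, against the stated 10% and 80%; the stated figures are met at 57. Passing supports at most a 12-week rate above 55%. It does not support 66%, and at a count of exactly 56 it does not support a rate above 55% at one-sided 10%. The results assume independent binomial outcomes, exactly 55 and 92 evaluable patients, and continuation at 32 or more, a reading confirmed by the 63% stopping probability. The planned size of 92 is consistent with the design and is not in question.

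**What to change.** In the Study Summary and Section 10.1, delete the conclusion that the true rate is at least 66% and replace the final rule with text such as:

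> A count of 57 or more successes among 92 evaluable patients rejects the null hypothesis of a 12-week progression-free rate of 55% or less (exact two-stage one-sided alpha 0.09998; power 0.803 at 66%). The estimate is reported with the exact two-stage p-value, the matching one-sided 90% lower bound and an exact two-sided 95% confidence interval based on stagewise ordering.

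The alternative is to keep 56 and restate alpha as 13.6% and power as 84.3% in the Study Summary and Sections 10.1 and 10.2. Choose between the two without reference to the final count. If the count is already known, say so and report the result against both cut-offs. Either way, give the exact two-stage p-value (0.136 at 56, 0.09998 at 57) and recompute the operating characteristics if the evaluable numbers differ from 55 and 92.

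The cost is a few sentences, with no new patients or data. The claim becomes less favourable. With 57, a final count of exactly 56 is no longer a success, and power returns from 84.3% to the planned 80%.
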